### **Objectives**

The overall aim of this project is to increase access to simplified medical abortion.

- To compare face-to face counseling with counseling through telemedicine in medical abortion with regard to efficacy (defined as complete abortion without on-going pregnancy or surgical intervention for incomplete abortion) evaluated 30 days after the abortion treatment based on patient follow up reports of low sensitivity uhCG, and patient records
- evaluation of safety, acceptability, surgical interventions, contraceptive uptake and unscheduled contacts.

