### 4. Outcome measures

# Primary outcome

Efficacy of medical abortion defined as complete abortion without ongoing intrauterine pregnancy or surgical intervention for incomplete abortion within 30 days of the abortion treatment. The outcome will be determined based on the home low sensitivity uhCG and patient records (surgical intervention).

Secondary outcomes will include safety (AE/SAE), any additional medical treatment of incomplete abortion, bleeding days and estimated amount, infection, surgical treatment for other indications than ongoing pregnancy or incomplete abortion, unscheduled contacts and visits, acceptability with the abortion counselling and treatment (in-clinic or self managed, self reported /estimated gestational length and contraceptive choice.

Incomplete abortion will be defined as products of conception remaining in the uterus with continued bleeding, bulky uterus, and open cervix at examination, possibly necessitating surgical evacuation at the discretion of the provider or at the woman's request derived from patient records.

Adverse events (AEs) will be recorded. The completeness of the abortion and any AEs will be identified by the on line follow up and by clinical examination.

Data management will be organized locally by data entry personnel and at the WHO centre, Karolinska. Data will be entered by use of a clinical trial software, checked for accuracy, and corrected after consultation of clinical records and research assistants, and reviewed monthly by the Study Coordinator at the WHO centre with further checking of clinic records as necessary.

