# Acceptability will be determined by responses to the following questions (evaluated at FU):

- 1. If you ever were to have another termination of pregnancy, would you opt for the same method of counselling? Yes/No/Doesn't matter
- 2. If you ever have another termination of pregnancy, would you prefer the counselling at the healthcare facility or to be responsible for your own counselling via telemedicine? 1 or 2
- 3. If you've previously had an abortion, how would you compare your experience this time with your previous treatment? Much worse, Worse, Similar, Better, Much better
- Acceptability of counselling procedure

Women will be asked to rate acceptability of counselling from 1 to 4

- 1, completely acceptable;
- 2, fairly acceptable;
- 3, fairly unacceptable;
- 4, completely unacceptable.

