### 8. Statistical analysis plan; power calculations - sample size

Sample size

The hypothesis to test is a non-inferiority hypothesis. The aim is to prove that telemedicine counseling is not inferior compared to standard abortion treatment. The expected efficacy rate (primary outcome) is 97.5% in both groups. The non-inferiority margin is set at 3%. The primary hypothesis will be tested by constructing a 95% confidence interval (CI) for the difference between the two treatments (intervention-control). If the upper limit of the CI is less than 3% the intervention will be declared as non-inferior to standard abortion care. In total 635 patients per group (1370 in total) is needed to obtain a power of 90%. To compensate for a 10% loss to FU an additional 138 women will be added to include 754 patients per group (total 1508 women).

Numbers and proportions of women having failed abortion and surgical intervention for incomplete abortion will be calculated by intervention. Both interventions will be compared using both absolute and relative measures with 95% confidence intervals. An intention-to-treat analysis as well as a per-protocol analysis will be performed. To evaluate the differences between the groups regarding independent nominal data such as side-effects and compliance, the chi squared test will be used. Continuous variables with a normal distribution, will be analysed using the Student's t-test whereas variable which are not normally distributed, such as age, GA (self-estimate vs LMP vs US) will presented as medians (range) and compared using Mann-Whitney U-test. Discrete numerical variables such as parity and bleeding days will be presented as means (range) and assessed for normality and comparison using the t-test or the Mann-Whitney U-test. Numeric variables (time lost from work and number of unplanned visits/consultations) will be analysed using analysis t-test. Results will be considered statistically

significant if P-value < 0.05. An independent data and safety monitoring committee will evaluate AE/SAE and make decisions if the trial should be stopped or continue as planned. Reason for stopping the trial could be a high failure rate or low acceptability rate in the intervention group. The plan for analysis and the study protocol has been developed in collaboration with prof. [name], Statisticon AB.

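### Secondary outcomes, including four acceptability items, all fall under one P < 0.05 rule with no hierarchy, adjustment or exploratory label

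*Combined protocol and SAP*

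**What the plan says.** The primary analysis is clearly set apart. Section 8 states: "The primary hypothesis will be tested by constructing a 95% confidence interval (CI) for the difference between the two treatments (intervention-control"), with a margin of 3 percentage points and an expected efficacy of 97.5% in each arm.

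The Objectives add "evaluation of safety, acceptability, surgical interventions, contraceptive uptake and unscheduled contacts". Section 4 then lists the secondary outcomes, beginning: "Secondary outcomes will include safety (AE/SAE), any additional medical treatment of incomplete abortion, bleeding days and estimated amount, infection". The list goes on to surgery for other indications, unscheduled contacts and visits, acceptability, gestational length and contraceptive choice. The acceptability section ("Acceptability will be determined by responses to the following questions (evaluated at FU") has three numbered questions and a separate rating from 1 to 4. None of the four is named as the main one.

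For analysis, section 8 assigns chi-squared, t or Mann-Whitney tests by type of variable. The variables to be compared include "variable which are not normally distributed, such as age, GA", as well as parity. The tests are followed by one criterion for all of them: results count as statistically "significant if P-value < 0.05".

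**The concern.** A blanket significance rule is more than silence on multiplicity. It tells the analyst to attach the word significant to any secondary comparison that crosses 0.05, whichever one it is and in either direction. A chance difference in infection, bleeding, contacts or acceptability could then appear beside the efficacy result as an established effect of telemedicine counselling, and nothing in the plan would tell the reader that it is unprotected.

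Acceptability is the sharpest case. It is a stated objective, it has four items, and the plan does not say which of them would support a claim.

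Testing age and parity between arms is a related weakness. Both are fixed before allocation, so in the full randomised set any difference between arms is due to chance. A test can only flag that chance difference.

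**Working it through.** **The plan's own figures.** The plan states no familywise error rate, so there is none to reproduce. Its sample size shows what the design protects. With 97.5% in both arms, a margin of 0.03, one-sided 0.025 and 90% power:

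n = 2 × 0.975 × 0.025 × (1.960 + 1.282)² / 0.03², which gives 570 per group after rounding up.

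With a continuity correction, (570/4) × [1 + √(1 + 4/(570 × 0.03))]² = 634.9, which matches the plan's 635 per group. The design is therefore built on one primary test. The secondary outcomes play no part in it.

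**Number of secondary tests (assumed).** Section 4 gives nine outcomes besides acceptability: AE/SAE, additional medical treatment, bleeding days, bleeding amount, infection, other surgery, unscheduled contacts and visits, gestational length, and contraceptive choice. The four acceptability items bring the total to 13. The count depends on choices. If gestational length is read as a comparison of dating methods and not of arms, it is 12. If AE and SAE are then tested separately, it is 13 again.

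**Formula.** Each test is taken as two-sided at 0.05 (the plan does not state sidedness), with no true difference on any outcome. For k independent tests the chance of at least one P < 0.05 is 1 − 0.95^k:

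- k = 4: 1 − 0.95⁴ = 1 − 0.8145 = 18.5%
- k = 12: 1 − 0.95¹² = 1 − 0.5404 = 46.0%
- k = 13: 1 − 0.95¹³ = 1 − 0.5133 = 48.7%
- k = 14: 1 − 0.95¹⁴ = 1 − 0.4877 = 51.2%

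For correlated tests, Z_j = √ρ·U + √(1−ρ)·E_j with U and E_j independent standard normal. The error is the share of draws in which any |Z_j| exceeds 1.96, from at least 200,000 draws per case.

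| Tests | ρ = 0 | ρ = 0.3 | ρ = 0.5 | ρ = 0.8 |
|---|---|---|---|---|
| 4 acceptability items | 18.5% | 17.3% | 15.6% | 11.3% |
| 13 secondary comparisons | 48.7% | 41.9% | 33.3% | 19.1% |

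With 12 tests the figures are 46% at ρ = 0 and 32% at ρ = 0.5, so the count of 12 or 13 hardly matters. The expected number of false positives does not depend on correlation: 4 × 0.05 = 0.20 and 13 × 0.05 = 0.65.

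Tests of rare events such as SAEs usually reject less often than 5%, so the true figures for the wider family would be somewhat lower.

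**The case against.** The best defence is that the trial's conclusion is already protected. There is one primary outcome, one non-inferiority test and one powered comparison; everything else is labelled secondary, and no confirmatory secondary claim is planned. This stands as far as the primary result goes. It does not settle the secondary outcomes, because section 8 applies its significance rule without regard to that label. The absolute and relative measures with 95% intervals that it promises are described for failed abortion and surgical intervention, not for the secondary list.

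Second, the test counts are constructed, and no test is expressly tied to acceptability. This also stands. Four acceptability tests are an inference from the blanket rule and from the provision for nominal data. Two items fit the model poorly: question 1 refers to a different method in each arm, and question 3 applies only to women with a previous abortion. The figures are therefore illustrative ranges.

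Third, a reader might infer that the plan breaches a promised 5% familywise rate. The documents do not support that: 0.05 is a criterion for each result, and no familywise rate is offered. A reader might also count the possible stopping for low acceptability as a further source of error. That sentence describes a committee's judgement about the intervention group and not a between-arm P-value, so it adds nothing to this calculation.

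Finally, age and parity differences are purely chance only in the full randomised set. A per-protocol subset could differ for other reasons. A significance test is still not needed to describe them.

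**Conclusion.** The concern holds in a limited form. The plan labels any comparison with P < 0.05 as statistically significant, and the available text gives no hierarchy, adjustment or exploratory status for the secondary outcomes. (That text passes from section 8 to section 10, so section 9 could not be checked.)

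With no true differences, the chance of at least one false label is about 16–19% for four acceptability items and 33–49% for 13 comparisons, at correlations from 0.5 to 0. It is lower with stronger correlation or rare events.

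A reader might conclude that a false secondary finding is likely. The figures do not support this: with equal 5% tests, the chance passes one half only from 14 fully independent tests. Nor is the non-inferiority test or its sample size affected. This is a worthwhile, inexpensive improvement to the plan and does not threaten its main result.

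**What to change.** In section 8, replace the sentence with the P < 0.05 rule by a statement along these lines: the non-inferiority test of the primary outcome is the only confirmatory test; all secondary outcomes, including every acceptability item, are exploratory and will be reported as between-group differences with 95% confidence intervals, unadjusted for multiplicity and without claims of statistical significance. Bring the sentences that assign tests by variable type into line with this.

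Present baseline variables such as age and parity descriptively by arm, with no between-arm test.

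If the sponsor wants a confirmatory acceptability claim, it should name one lead item of its own choosing in advance and test it only after non-inferiority has been shown. The documents give no ground for preferring one of the four items.

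The cost is a few sentences, with no new data, no extra participants and no change to the primary test. The downside is that secondary differences can no longer be announced as statistically significant.

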# 10. Ethics committees and other regulatory boards

Approved by the EPN/EPM .Also submitted to the personal data officer at the University Hospital.

# **Significance**

Worldwide it is estimated that around 56 million pregnancies are terminated each year. In countries where women lack access to safe abortion care, unsafe abortion is a significant cause of maternal mortality and morbidity. As many as 19 million women experience an unsafe abortion (18.5 million of these occur in developing countries) and approximately 13% of all maternal deaths are due to complications of unsafe abortion.

Unintended and unwanted pregnancies are a global reproductive health problem. It undermines women's schooling, health, social status and future opportunities for work. This contributes to their unequal status in society and is directly linked to poverty.

Giving women access to safe and effective contraceptive methods and safe abortion care, improves family well being and reduces abortion rates as well as maternal mortality.

Access to essential medicines is a human right. The World Health Organization's definition of health is: "Health is a state of complete physical, mental and social well-being and not merely the absence of disease or infirmity" (from the preamble of the constitution of the World Health Organization, which was adopted in 1946 by all members of the World Health Organization).

Article 12 of the *International Covenant on Economic, Social and Cultural Rights* states that the right to health includes a right to enjoy available, accessible and acceptable health care consisting of a variety of goods and services necessary for the realization of the highest attainable standard of health. Goods and services related to pregnancy and its termination, including essential medicines, are necessary to the realization of the highest attainable standard of reproductive health.

Women worldwide use the internet to find information about abortion services. However, very little is known about the way women obtain information about medical abortion and their experiences doing medical abortions by themselves especially in countries where abortion is legally restricted. This study is conducted to increase access to medical abortion via telemedicine which if implemented could be a tool to reduce maternal mortality and morbidity.

